APPENDIX 1 – PATIENT QUESTIONNAIRE & INTERVIEW

8.1 Demographic Survey (CHF Cohort – Pre)

- What is your gender?
 1. Female
 2. Male
 3. Other (specify) : _____
- Do you consider yourself to be of Hispanic, Latino/a, or Spanish origin?
 1. Yes
 2. No
- Which racial group or groups do you consider yourself to be in?
 1. American Indian or Alaska Native
 2. Asian
 3. Black or African American
 4. Native Hawaiian or Other Pacific Islander
 5. White
 6. Other
- What is the highest degree or education level you have completed?
 1. Some high school
 2. High School
 3. Some college/Associate's degree
 4. Bachelor's degree
 5. Master's degree or higher
 6. Prefer not to say
- What is your marital status?
 1. Single
 2. Married
 3. Separated
 4. Divorced
 5. Widowed
- How many people live in your household with you?
- What was your total household income before taxes during the past 12 months?
 1. Less than \$25,000.
 2. \$25,000 to \$34,999.
 3. \$35,000 to \$49,999.
 4. \$50,000 to \$74,999.
 5. \$75,000 to \$99,999.
 6. \$100,000 to \$149,999.
 7. \$150,000 or more

8.2 Self-Care Self-Efficacy Scale (CHF– Pre and Post)

In general, how confident are you that you can:

(Circle **one** number for each statement)

1. Keep yourself stable and free of symptoms?	1	2	3	4	5
2. Follow the treatment plan you have been given?	1	2	3	4	5
3. Persist in following the treatment plan even when difficult?	1	2	3	4	5
4. Monitor your condition routinely?	1	2	3	4	5
5. Persist in routinely monitoring your condition even when difficult?	1	2	3	4	5
6. Recognize changes in your health if they occur?	1	2	3	4	5
7. Evaluate the importance of your symptoms?	1	2	3	4	5
8. Do something to relieve your symptoms?	1	2	3	4	5
9. Persist in finding a remedy for your symptoms even when difficult?	1	2	3	4	5
10. Evaluate how well a remedy works?	1	2	3	4	5

8.2.1.1.1.

© [name]

Device related questions:

In general, how confident are you that you can:

1. Continuously wear the device for 30 days?
2. Follow the research study protocol for 30 days?

8.3 MLHFQ (CHF Cohort – Pre and Post)

The following questions ask how much your heart failure (heart condition) affected your life during the past month (4 weeks). After each question, circle the 0, 1, 2, 3, 4 or 5 to show how much your life was affected. If a question does not apply to you, circle the 0 after that question.

Did your heart failure prevent you from living as you wanted during the past month (4 weeks) by -	No	Very Little			Very Much	
		1	2	3	4	5
1. causing swelling in your ankles or legs?	0	1	2	3	4	5
2. making you sit or lie down to rest during the day?	0	1	2	3	4	5
3. making your walking about or climbing stairs difficult?	0	1	2	3	4	5
4. making your working around the house or yard difficult?	0	1	2	3	4	5
5. making your going places away from home difficult?	0	1	2	3	4	5
6. making your sleeping well at night difficult?	0	1	2	3	4	5
7. making your relating to or doing things with your friends or family difficult?	0	1	2	3	4	5
8. making your working to earn a living difficult?	0	1	2	3	4	5
9. making your recreational pastimes, sports or hobbies difficult?	0	1	2	3	4	5
10. making your sexual activities difficult?	0	1	2	3	4	5
11. making you eat less of the foods you like?	0	1	2	3	4	5
12. making you short of breath?	0	1	2	3	4	5
13. making you tired, fatigued, or low on energy?	0	1	2	3	4	5
14. making you stay in a hospital?	0	1	2	3	4	5
15. costing you money for medical care?	0	1	2	3	4	5
16. giving you side effects from treatments?	0	1	2	3	4	5
17. making you feel you are a burden to your family or friends?	0	1	2	3	4	5
18. making you feel a loss of self-control in your life?	0	1	2	3	4	5
19. making you worry?	0	1	2	3	4	5
20. making it difficult for you to concentrate or remember things?	0	1	2	3	4	5
21. making you feel depressed?	0	1	2	3	4	5

©1986 Regents of the University of Minnesota, All rights reserved. LIVING WITH HEART FAILURE® is a registered trademark of the Regents of the University of Minnesota.

Image Source: http://license.umn.edu/technologies/94019_minnesota-living-with-heart-failure-questionnaire-mlhfq

8.4 EHFScB-9 (CHF Cohort – Pre and Post)

5 point Likert scale (1=I completely agree... 5=I do not agree at all)

- I weigh myself every day.
- I contact my doctor or nurse if my shortness of breath increases.
- I contact my doctor or nurse if my feet/legs become swollen.
- I contact my doctor or nurse if I gain 5 pounds in 1 week.
- I limit the amount of fluids I drink.
- I contact my doctor or nurse If I experience increased fatigue.
- I eat a low salt diet.
- I take my medications as prescribed.
- I exercise regularly.

Enrichd Social Support Instrument (CHF cohort – Pre)

Appendix 1 • ENRICHD SOCIAL SUPPORT INSTRUMENT (ESSI)

Please read the following questions and circle the response that most closely describes your current situation.

1. Is there someone available to you whom you can count on to listen to you when you need to talk?

None of the time A little of the time Some of the time Most of the time All the time

2. Is there someone available to give you good advice about a problem?

None of the time A little of the time Some of the time Most of the time All the time

3. Is there someone available to you who shows you love and affection?

None of the time	A little of the time	Some of the time	Most of the time	All the time
1	2	3	4	5

4. Is there someone available to help you with daily chores?

None of the time A little of the time Some of the time Most of the time All the time

5. Can you count on anyone to provide you with emotional support (talking over problems or helping you make a difficult decision)?

None of the time A little of the time Some of the time Most of the time All the time

6. Do you have as much contact as you would like with someone you feel close to, someone in whom you can trust and confide?

None of the time A little of the time Some of the time Most of the time All the time

7. Are you currently married or living with a partner?

Yes

No

402 / Journal of Cardiopulmonary Rehabilitation 2003;23:398-403

8.5 Monitoring Process Random Question Bank

Week 1

I had difficulty learning to use the devices.

- Not at all
- A little bit
- Somewhat
- Quite a bit
- Very much

I felt safe being monitored through the system.

- Not at all
- A little bit
- Somewhat
- Quite a bit
- Very much

Week 2

I experienced problems with the patch.

- Not at all
- A little bit
- Somewhat
- Quite a bit
- Very much

I felt reassured seeing my data on the phone.

- Not at all
- A little bit
- Somewhat
- Quite a bit
- Very much

Week 3

I experienced problems with the phone application.

- Not at all
- A little bit
- Somewhat
- Quite a bit
- Very much

I felt more self-conscious of my symptoms as a result of the monitoring.

- Not at all
- A little bit
- Somewhat

- Quite a bit
- Very much

Week 4

Using the system requires a lot of technical support.

- Not at all
- A little bit
- Somewhat
- Quite a bit
- Very much

Using the devices helped me overall.

- Not at all
- A little bit
- Somewhat
- Quite a bit
- Very much

Week 5

I am excited to be using a device to monitor my health.

- Not at all
- A little bit
- Somewhat
- Quite a bit
- Very much

I think using devices to monitor my health is an advance in modern medicine.

- Not at all
- A little bit
- Somewhat
- Quite a bit
- Very much

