Patient enrollment (prior to discharge): Following a detailed presentation of the device and study, and informed consent, researchers will administer a questionnaire to establish the participant's comfort and experience level with a wearable device (e.g., habitual use of a wrist-worn activity monitoring device) and to ascertain that the participant has understood the limitations of the devices (e.g. that they provide continual but not constant, "real-time" monitoring) prior to hospital discharge. This will be followed by an in-person semi-structured interview for first 20 patients who agree to interviews from each cohort. We will refer to the 20 patients with interview in each cohort as the first patient group, and the enrolled patients with no interviews as the second patient group. The interview is informed by A/TAM to establish the patient's readiness to use a wearable device as a means of monitoring their post-discharge status, including to establish any anticipated challenges in technology-mediated interaction with the care team; and finally, to identify any knowledge gaps that may need to be filled through the induction process. Paradata will be collected at the interview to assist with analysis. We would like to stress that only the first patient group from each cohort will receive pre and post-study interviews. The second patient group enrolled in each cohort will not participate in interviews. Researchers will only administer required surveys at different time points for the 2nd patient group.

Patient progress (throughout the period of device use): Monitoring of the patient's experience and satisfaction with the device and the study process will be combined with weekly monitoring questions focusing on the following aspects: **(a)** experience with physical use and tolerance of the device; assess any difficulty in keeping it in place, any skin reaction, possible somatization of health concerns; **(b)** experience of self-monitoring and communication with care team through the device **(c)** degree of reassurance or

anxiety about the patient's recovery process; finally, **(e)** paradata from device and interaction metrics, including possible sentiment analysis of interaction text.

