4.3 Informed Consent Procedure

4.3.1 Patients

The research coordinator is responsible for explaining the study to potential and willing participants. The consent process begins once the participant is interested in being enrolled in the study. At this time, the research coordinator will conduct a thorough review of the consent details, including study procedure, risks, confidentiality, etc. with the potential participants. Participants will be given adequate time to think about their decision to participate without under coercion on the part of the researchers. Whether a patient wishes or not, to be enrolled, that patient's medical care will not be affected. No consent will be completed if the participants have unanswered questions, and potential participants may talk over the details with the consent with whomever they wish, prior to giving consent.

Participants will need to be consented in a face-to-face meeting with the research coordinator and if they wish to obtain a copy of the consent, they are free to do so. If there is a change in the consent during ongoing study activities, the participant may be asked to re-consent, if changes will have a direct effect on the participant.

The plan is to enroll a total 20 patients. During patient recruitment, if any of the first approached eligible patients from each cohort expresses interest in the study but is unwilling to participate in interviews, the research coordinator will present the no-interview consent form to patients as an alternative option. Once the no-interview group is full, patients will only be presented the consent form with interviews.

As part of the informed consent process:

1. The participant agrees to wear a total of 5 VCI VitalPatch for 7 days each adding up to 35 total days of monitoring. The research coordinator will place the VitalPatch on patients when they are still hospitalized. Our goal is to collect 30 days of post-discharge data.
2. The participant agrees to replace the VitalPatch every 7 days and to answer survey questions either daily (in the morning) or twice a day for the duration of the study in a timely fashion
3. The participant agrees to follow directions on the pinpointIQ application

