6.4 Regulatory Status

This study is considered a non-significant risk (NSR) Investigational Device Exemption (IDE) study according to 21 CFR §812.2(b) to evaluate the clinical utility of PhysIQ vital patch solution. All FDA-cleared devices in pinpointIQ will be used according to their intended use. The components of this system and clearance status are described below:

1. VitalPatch wearable biosensor: FDA 510k-cleared Class II-regulated medical device – Vital Signs Biosensor (K190916)
2. PhysIQ Cloud-based IT platform (physIQ mobile app, IT platform, Clinician User Interface): FDA Class I-regulated medical device – Medical device data system

3. PhysIQ Personalized Physiology Analytics: FDA 510k-cleared Class II-regulated medical device – Multivariate Change Index ([K142512](#))
4. PhysIQ feature analytics: FDA 510K cleared Class II-regulated medical device – heart rate, heart rate variability, respiration rate and atrial fibrillation detection ([K183322](#))
5. PhysIQ actigraphy analytics: FDA Class-I-regulated medical device – walking, steps, posture, sleep, body tilt, gross activity, activity stratification.

- **Potential Risks and Benefits**

When used in accordance with the clinical protocol, risks associated with pinpointIQ are considered low. To ensure proper use of the solution, subjects, patients and providers will be trained in accordance with the manufacturer's instructions for use. In addition, clearly defined study eligibility criteria have been established to ensure that only appropriate patients are enrolled in the study.

The potential risks of VitalPatch may include the following: adverse skin reactions, skin irritations, mild soreness, redness (see attached IFU).

- **Device Packaging, Labeling and Use**

The VitalPatch™ and mobile phone will be shipped as a kit to NorthShore in the care of the PI/research coordinator. Device components will be labeled "For Prescribed Use in a Clinical Trial" and packaged by physIQ according to applicable regulations. Upon completion of data collection, the subject will mail back all study equipment in a pre-paid mailer that was provided in the kit. PhysIQ and NorthShore research team will maintain device accountability records for each study site and for each subject enrolled, pursuant to 21 CFR§812.110 and Good Clinical Practices (GCP).

BIBLIOGRAPHY

1. Hospital Readmission Reduction Program, Patient Protection and Affordable Care Act, Vol [S]3025 2010

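### Section 3.2 promises weekly questions on patch tolerance including skin reaction, but the weekly question bank in 8.5 has one general patch item and none on skin or adhesion

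*Protocol*

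**What the plan says.** Protocol section 3.2, under Patient progress, covers the whole period of device use. It says that monitoring of the patient's experience "will be combined with weekly monitoring questions focusing on the following aspects". The first aspect is physical use and tolerance of the device, where the stated task is to "assess any difficulty in keeping it in place, any skin reaction, possible somatization of health concerns".

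Section 8.5 (Monitoring Process Random Question Bank, Appendix 1) sets out items for weeks 1 to 5, two per week, each with the same five-step answer scale. The item on the patch is in week 2: "I experienced problems with the patch". The nearest other device item is in week 1: "I had difficulty learning to use the devices".

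Section 6.4 gives the potential risks of the VitalPatch as "adverse skin reactions, skin irritations, mild soreness, redness" and refers to attached instructions for use.

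On exposure and sample, section 4.3.1 (Patients) states "The participant agrees to wear a total of 5 VCI VitalPatch for 7 days each adding up to 35 total days of monitoring" and "The plan is to enroll a total 20 patients".

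**The concern.** Section 3.2 commits to collecting specific information and section 8.5 is the tool supplied to collect it. The tool omits two of the things named: skin reaction and trouble keeping the patch in place. Skin reaction is also the kind of harm that section 6.4 attaches to the device, and section 4.2.1 treats it as relevant by excluding patients with adhesive allergy or existing skin damage.

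At stake is whether the study can say how many patients had a skin reaction and when. A patient who rates patch problems on a general scale in week 2 may mean itching, a patch that fell off, a flat battery or a failed pairing. That answer gives no count of skin reactions. Mild reactions not recorded at the time are also hard to recover reliably afterwards, and in a sample of 20 each one changes the observed proportion by 1/20 = 5 percentage points.

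**Working it through.** The plan gives no figure to reproduce. The check is a count of items, a comparison with section 3.2, and a search of the other instruments.

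**Step 1. Count the weekly bank (section 8.5).**

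| Week | First item (topic) | Second item (topic) | Patch problem? | Skin or adhesion? |
|---|---|---|---|---|
| 1 | learning the devices | feeling safe | no | no |
| 2 | patch problems | reassurance from own data | yes | no |
| 3 | phone application problems | self-consciousness about symptoms | no | no |
| 4 | need for technical support | overall help | no | no |
| 5 | enthusiasm | view of the technology | no | no |

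Total items: 5 weeks × 2 = 10. Patch-problem items: 1 of 10, in 1 of 5 weeks. Skin or adhesion items: 0 of 10, in 0 of 5 weeks.

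**Step 2. Compare with the topics in section 3.2.** Somatization has a plausible counterpart in week 3, and reassurance has counterparts in weeks 1 and 2. Skin reaction and keeping the patch in place have none. The gap is therefore specific to these two topics.

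**Step 3. Look for the missing topics elsewhere in the protocol.**
- Daily app questions and monitoring-nurse template (section 2.2, Tables 1 and 2): heart failure and general symptoms, weight, medication, diet and alerts. No skin item.
- Mid-level note template (Table 3): rash appears once, as an example of a sign of infection, in a note used when care is escalated. It does not ask about the patch site.
- Self-efficacy questions (8.2): confidence in wearing the device for 30 days. No skin item.
- Endpoint survey (8.6): the patch items concern convenience, replacement, sense of security and doubts about future use. No skin item.
- Endpoint interview (8.7.2): one open question on the device, with a general probe on the patch and phone. No skin probe, and only the interview group receives it.

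**Step 4. Express the coverage in patient-weeks.** Inputs: 20 patients (4.3.1) and 5 weekly prompts (8.5). Assume that every patient completes all five prompts and sees both items each week.
- Patient-weeks: 20 × 5 = 100.
- General patch item: 20 × 1 = 20 of 100.
- Skin-reaction item: 20 × 0 = 0 of 100.
- With a skin item in each weekly prompt: 20 × 5 = up to 100 of 100.

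The heading of 8.5 calls the bank random without saying how items are drawn. If one of the two weekly items were drawn with equal probability, about 20 × 1/2 = 10 patients would see the patch item at all. The skin count stays at 0 either way.

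**The case against.** Four points on the other side deserve weight.

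First, section 3.3.1 introduces Appendix 1 as an example of potential questions, so the final bank may differ. That is true, and it softens the finding. However, 8.5 gives a week, a wording and an answer scale for every item, and the protocol contains no other weekly set that would meet section 3.2.

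Second, section 3.2 can be read as listing topics for the monitoring as a whole, since its list also includes paradata, which is not a patient question. On that reading, rotating items are acceptable and asking about the patch only in week 2 is no breach. What remains is the absence of the skin and adhesion topics, which does not depend on the reading.

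Third, a reader might infer from the week 2 timing that the third to fifth patches are never asked about. The documents do not support this. The endpoint survey and the endpoint interview both ask about the patch after the full wear period. Under section 3.2 the interview group is the first 20 patients who agree, against 20 planned in total, so it could be a large part of the sample, although 4.3.1 also allows enrolment without interviews. These questions can bring out a skin complaint; they do not ask for one.

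Fourth, a reader might infer that tolerability is a stated aim and that a calculable share of reactions would be missed. Neither holds. The aims in 2.1 and 3.1 concern thresholds and workflows, prediction, care processes, return on investment, feasibility, usability, effectiveness, and patient acceptance, perceptions and satisfaction. Section 3.2 mentions subjective tolerability only as an example of a hypothesis for further study. The protocol gives no per-patch reaction rate, so any missed share would rest on an assumed rate and would mostly restate that three of five patches follow week 2.

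Incidental routes also exist, such as complaints volunteered by patients or coordinator calls about device non-use (4.7). They are unsystematic and do not supply a denominator.

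**Conclusion.** Sections 3.2 and 8.5 do not agree. Section 3.2 says the weekly questions assess skin reaction and difficulty keeping the patch in place; the weekly bank has 0 of 10 items on either and 1 of 10 on patch problems in general. No other instrument shown fills the gap, so the local effects listed in 6.4 are not systematically recorded.

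This is a modest measurement gap in a small study. It leaves the readmission and workflow aims untouched and does not show that the device is poorly tolerated. It means that the protocol as laid out could not support a statement on how often skin reactions occurred.

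The item counts need no assumption. The patient-week figures assume 20 enrolled patients, full completion and both items shown each week. The conclusion about recording is limited to the instruments in the protocol; the attached instructions for use are not available here.

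**What to change.** Reconcile sections 3.2 and 8.5. Add to each of the five weekly prompts one short yes/no patch-tolerance item that names skin reaction explicitly, with trouble keeping the patch on as a separate tick so that a positive answer can be attributed. Keep the existing rotating items. State in 8.5 whether every patient receives the fixed item and how the rotating items are drawn.

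Report the answers descriptively: for each week, the number answering yes over the number who answered, with non-response shown; and overall, the number of patients with at least one yes. No test is needed.

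The cost is one extra item per week in the app and a revised appendix. Sample size, visits and the other instruments do not change.

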3.1 Qualitative Research Aims

Receive provider and patient feedback on the application of wearable technology to post-discharge care to conduct a theory-driven evaluation of feasibility, usability, and effectiveness. We will address motivational and self-care issues at baseline, continuing and post-study from both providers and patients' viewpoints. 1) ascertain perceptions of telemonitoring and remote patient management of high-risk patients, of organization and effectiveness of care by providers using interviews and surveys; and 2) evaluate patient acceptance, perceptions of and satisfaction with wearable patches, with prompted requests for patient status information, and with escalation pathways for nurse navigators and physicians using interviews and survey tools.

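### No weekly patient question is asked twice, so the weekly items cannot follow tolerance or reassurance over the period of device use

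*Protocol*

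**What the plan says.** Section 3.1 of the protocol sets the aim: "We will address motivational and self-care issues at baseline, continuing and post-study". Section 3.2, part II, under patient progress, says that monitoring of experience and satisfaction during device use "will be combined with weekly monitoring questions focusing on the following aspects". The aspects listed are physical use and tolerance of the device (keeping it in place, skin reaction), self-monitoring and communication with the care team, and reassurance or anxiety about recovery.

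The only schedule given for these questions is in Appendix 1, under the heading "8.5 Monitoring Process Random Question Bank". It prints two items under each week:

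- Week 1: "I had difficulty learning to use the devices" and "I felt safe being monitored through the system".
- Week 2: "I experienced problems with the patch" and an item on reassurance from seeing one's data.
- Week 3: "I experienced problems with the phone application" and an item on self-consciousness about symptoms.
- Week 4: an item on the need for technical support and one on overall help.
- Week 5: "I am excited to be using a device to monitor my health" and an item on such devices as progress in medicine.

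No item appears under a second week, and no random order or rotation is described for patients.

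**The concern.** Following a patient's experience through a period of use needs at least one question put more than once. Here each question belongs to one week. If answers look better or worse in week 4 than in week 2, the reader cannot tell whether the experience changed or only the question did.

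The gap touches the aspects that section 3.2 names. A participant wears five patches in turn (section 4.3.1), but the patch-problem item falls in week 2 only, so trouble that begins with the third, fourth or fifth patch is outside it. Feeling safe is asked once at the start, and reassurance from the data once in week 2. With 20 patients, weekly answers that were not collected cannot be recovered later.

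The heading adds an ambiguity. A random bank and a fixed weekly list are different designs, and whoever programs the app has to guess which is meant.

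**Working it through.** The protocol gives no sample size, power or error rate for the weekly questions, so there is no figure to reproduce. The check is structural.

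**Inputs**
- Items: 10, two per week, none repeated (section 8.5).
- Weeks: 5 (section 8.5).
- Patients: 20 (section 4.3.1).
- Patches: 5 of 7 days each, 5 × 7 = 35 days of monitoring (section 4.3.1). The monitoring period is given as 30 days in sections 2.1 and 4.4.1.

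**Can item and week be separated?** Take an additive model with an intercept, 9 item contrasts and 4 week contrasts: 1 + 9 + 4 = 14 columns. The rank of the design is items + weeks − (number of unconnected item-week blocks).

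| Schedule | Answers (20 patients) | Unconnected blocks | Rank | Week contrasts separable from items |
|---|---|---|---|---|
| As printed | 20 × 10 = 200 | 5 | 10 + 5 − 5 = 10 of 14 | 0 of 4 |
| As printed, plus the feeling-safe item every week | 20 × 14 = 280 | 1 | 10 + 5 − 1 = 14 of 14 | 4 of 4 |
| As printed, plus the feeling-safe and patch-problem items every week | 20 × 18 = 360 | 1 | 14 of 14 | 4 of 4 |
| Item pairs rotated over weeks by patient | 200 | 1 | 14 of 14 | 4 of 4 |

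Building each design matrix and taking its rank numerically gave the same values. The printed layout falls short by 14 − 10 = 4, which is every week contrast. One repeated item is enough to restore them under additivity. The course of the anchor item itself can be read off directly without that assumption.

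**Burden of two anchors.** Each anchor already appears once, so each adds 4 askings: 2 × 4 = 8 over five weeks. Weeks 1 and 2 go from two questions to three, and weeks 3 to 5 from two to four. The addition is at most two per week.

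**Where week 5 falls.** Counted over 35 days of patches it is days 29 to 35; counted over a 30-day period from discharge it is days 29 and 30. The documents do not say which count applies. Section 6.1 also gives patch wear of up to 5 days beside a battery life of about 7 days. Five patches then cover 25 or 35 days, and these statements must be reconciled.

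**The protocol's own comparison.** For providers, section 3.2, part I, describes a recurring, partly randomised matrix of questions meant to give adequate coverage of questions, providers and patients. Nothing equivalent is described for patients.

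**The case against.** The strongest reply is that nothing planned depends on comparing weeks. Section 3.2 uses the items for monitoring, section 3.6 plans thematic coding of interviews, and no trend over weeks or contrast between items is proposed. Section 3.3.1 also calls the appendix questions examples, although that sentence speaks of the interview. Some content is covered elsewhere: self-efficacy, quality of life and self-care are measured before and after (sections 8.2 to 8.4), the endpoint survey returns to security, ease of use and satisfaction (section 8.6), and the endpoint interview asks how feelings changed over the month (section 8.7.2). Different items each week also spare patients who already answer daily questions.

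Much of this stands. No stated analysis is damaged, and continuing assessment is not wholly absent, since device and interaction paradata are collected too. But the endpoint sources look back, and only the first patient group is interviewed. They do not replace a weekly item that is repeated.

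Three stronger readings are tempting and are not supported:

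- That week 5 is only days 29 and 30. The 35 days of patches allow days 29 to 35.
- That only patients still wearing the patch answer in week 5. No section says so, none says that a readmitted patient stops answering, and the endpoint interview guide provides for readmitted patients. A count of those left to answer would rest on an assumption that the protocol does not make.
- That the item order builds in a shift from difficulty to enthusiasm. Problem-type items occur in each of weeks 1 to 4, and favourable ones in weeks 1, 2, 4 and 5. Only week 5 is wholly favourable.

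**Conclusion.** The point holds in a limited form. As printed, 0 of 10 items has a second time point and 0 of 4 week contrasts can be separated from the items, so the weekly questions cannot show the progress for which section 3.2 introduces them. The heading and the fixed layout also contradict each other. The consequence is confined to the interpretation of descriptive process data; no planned test, estimate or figure changes. The result rests on section 8.5 being the schedule actually used, and the rank argument on additive item and week effects. It is a minor point, worth acting on because the remedy is nearly free.

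**What to change.** 1. Reconcile the heading of section 8.5 with its layout, by dropping the word random or by describing how items are drawn.
2. Repeat one or two anchor items every week. Suitable choices are "I experienced problems with the patch" and "I felt safe being monitored through the system", which match the tolerance and reassurance aspects of section 3.2. Naturally timed items, such as difficulty in learning the devices, can stay in week 1. Full random rotation would also separate item from week, but would move such items to odd times and is not needed.
3. Also ask the two week-5 items by day 28 or in the endpoint survey, so that they do not depend on whether monitoring runs for 30 or 35 days, and state which count of days defines the weeks.
4. Report the number of patients answering each week beside the responses.

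The cost is a small change to the app schedule and up to two extra taps a week, 8 per patient in all if both anchors are used.
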